8.3.1 Phase 1b

All endpoints in the phase 1b part of the study will be analyzed as-is and no imputation is planned.

[REDACTED]

[REDACTED]

8.4 Detection of Bias

Important protocol deviations and early withdrawal from treatment and from study may bias the results of the study. The incidence of these factors will be assessed and reason for early withdrawals will be tabulated.

8.5 Outliers

Outlier data will not be excluded unless scientifically justified.

Pharmacokinetic (PK) serum concentration data will be evaluated for outliers by visual inspection, and decisions to re-assay individual samples will be made in accordance with standard pharmacokinetic evaluation practice.

8.6 Distributional Characteristics

Not Applicable

8.7 Validation of Statistical Analyses

Programs will be developed, maintained, and output will be verified in accordance with current risk-based quality control procedures.

Tables, figures, and listings will be produced with validated standard macro programs where standard macros can produce the specified outputs.

The production environment for statistical analyses consists of Amgen-supported versions of statistical analysis software; for example, the SAS System.

9. Statistical Methods of Analysis

9.1 General Considerations

Analyses of phase 1b data will be provided separately than analyses of phase 2 data. Descriptive statistics will be provided for selected demographics, safety, PK, PD, and biomarker data. Descriptive statistics on continuous measurements will include means, medians, standard deviations, and ranges, while categorical data will be summarized using frequency counts and percentages. Data will be presented and summarized by treatment and by time as appropriate. **Data collected at unscheduled visits or timepoints will be included in the analysis unless stated otherwise.**

Only critical subject-level data listings will be provided in the Clinical Study Report. Additional listings of subject-level data will be reviewed as part of DLRMs or ongoing data review for assessment of product's safety, efficacy and the quality of data, but will not be included in the Clinical Study Report.

9.2 Subject Accountability

Phase 1b [REDACTED]

The number and percent of subjects who were enrolled, received at least one dose of investigational product, completed investigational product, discontinued from investigational product (including reasons for discontinuing), completed study, discontinued the study (including reasons for discontinuing) will be summarized overall and by **treatment group**.

Key study dates for the first subject enrolled, last subject enrolled, and last subject's end of study will be presented.

A summary of number of subjects in each analysis subset will be provided.

9.3 Important Protocol Deviations

Phase 1b [REDACTED]

Important Protocol Deviations (IPDs) categories are defined by the study team before the first subject's initial visit and updated during the IPD reviews throughout the study prior to database lock. These definitions of IPD categories, subcategory codes, and descriptions will be used during the course of the study.

The final IPD list is used to produce the list of subjects with IPDs.

Eligibility deviations are defined in the protocol. A list of deviations from eligibility criteria will also be generated.

9.4 Demographic and Baseline Characteristics

The full analysis set will be used to summarize subject demographics and baseline disease characteristics.

Phase 1b [REDACTED]

9.4.1 Demographic

- Age (years) at enrollment (continuous summary statistics)
- **Age categories (number and percent of subjects in 18 – 64 and 65 - 70 years)**
- Sex (number and percentage of males and females)
- Ethnicity (number and percentage of Hispanic or Latino and Not Hispanic or Latino)
- Race (number and percentage of subjects in each race, or mixed-race combination)

9.4.2 Baseline Characteristics

- Height and weight (continuous summary statistics)
- Duration of RA (years) (continuous summary statistics)
- **Prior medication uses for RA indication (number and percentage of subjects)**
- **Time on Methotrexate (weeks) (continuous summary statistics)**
- **Average weekly Methotrexate dose (mg) (continuous summary statistics)**
- **Rheumatoid factor (continuous summary statistics)**
- **Anti-cyclic citrullinated peptide (anti-CCP) antibody value (continuous summary statistics)**

[figure not shown]
9.5 Efficacy Analyses

[figure not shown]
Table 9-1. Efficacy Endpoint and Analysis Method Table Endpoint	Primary Summary and Analysis Method (Specify Analysis Set if FAS is Not Used)	Sensitivity Analysis
Primary Endpoint		
Phase 1b: The primary endpoint of phase 1 is not an efficacy endpoint. [REDACTED]	ACR 20 at week 12	
Secondary Endpoints		
ACR 50/70 at week 12		
DAS28-ESR/CRP		

The full analysis set will be used for primary analyses of the primary and secondary efficacy endpoints unless otherwise specified. The analysis set to be used for sensitivity analysis will be specified in this section.

9.5.1 Analyses of Primary Efficacy Endpoint(s)

[figure not shown]
The primary endpoint for phase 1b is not an efficacy endpoint. The primary endpoint for [REDACTED] is ACR 20 at week 12.

[figure not shown]

9.5.2 Analyses of Secondary Efficacy Endpoint(s)

Phase1b does not include any secondary efficacy endpoints.

9.6 Safety Analyses

9.6.1 Analyses of Primary Safety Endpoint(s)

Phase 1b

The primary endpoint for phase 1b is safety. The analysis will include the descriptive summary statistics for adverse events, disease-related events, laboratory measures, vital signs, physical measurements and ECG. Details are described in respective section below.

9.6.2 Adverse Events

[figure not shown]
Phase 1b

The Medical Dictionary for Regulatory Activities (MedDRA) version 20 or later will be used to code all adverse events to a system organ class and a preferred term. The severity of each adverse event will be graded using CTCAE criteria version 4.0 or later (see [Appendix C](#)).

An overall summary of treatment-emergent adverse events by toxicity grade and type will be provided.

Subject incidence of all treatment-emergent, serious treatment emergent, treatment-related, **serious treatment-related**, adverse events leading to withdrawal of investigational product, and fatal adverse events will be tabulated by system organ class in alphabetical order and preferred term in descending order of frequency. **Treatment emergent adverse events and treatment-related adverse events will also be tabulated by preferred term and worst severity grade.**

Subject incidence of disease-related events will also be summarized **separately** for all treatment-emergent disease-related events and fatal disease-related events.

9.6.3 Laboratory Test Results

Phase 1b

Unscheduled assessments will be incorporated in the laboratory analyses where possible.

Summaries of chemistry and hematology laboratory data will include baseline value, values and change from baseline at scheduled visits.

Shift tables indicating the change between the baseline and the maximum post dose CTCAE grades **based on CTCAE version 4.0 or later** will be provided for selected laboratory parameters of interest.

A listing of normal ranges of lab analytes will be included. Further, a listing of CTCAE grade 3 or higher laboratory toxicities will be provided for subjects with grade 3 or higher toxicity for any of the parameters included in the shift table. This listing will include all available data for laboratory parameters included in shift table in order to provide proper context. Values outside the normal laboratory reference ranges will be flagged as high or low and corresponding CTCAE grades will be included in the listing.

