9.2.4 Clinical Laboratory Assessments

All screening and on-study laboratory samples will be processed and sent to the central laboratory with the exception of erythrocyte sedimentation rate (ESR), urine pregnancy, PPD, and Quantiferon (may be done by central or local laboratory). The central laboratory will be responsible for all screening and on-study serum chemistry,

hematology, serum pregnancy, urinalysis, hepatitis C antibody, hepatitis B surface antigen and core antibody, high sensitivity CRP, and any other laboratory tests required. ESR, urine pregnancy and PPD testing, if applicable, will be performed locally with kits provided by the central laboratory (except PPD). The results of this testing will be maintained in the source documents at the site.

Subjects in the phase 1b part of the study will abstain from strenuous exercise for 72 hours before each blood collection for clinical laboratory tests.

Amgen or designee will be responsible for biomarker and pharmacogenetic assessments, and the central laboratory will ship the samples to Amgen or a specialty laboratory for assay (depending on the assessment). The central laboratory will provide a study manual that outlines handling, labeling, and shipping procedures for all samples. All blood samples will be obtained by venipuncture before investigational product administration. The date and time of sample collection will be recorded in the source documents at the site.

Refer to [Appendix 2](#) for the list of clinical laboratory tests to be performed and to the Schedule of Activities for the timing and frequency.

The investigator is responsible for reviewing laboratory test results and recording any clinically relevant changes occurring during the study in the Event CRF. The investigator must determine whether an abnormal value in an individual study subject represents a clinically significant change from the subject's baseline values. In general, abnormal laboratory findings without clinical significance (based on the investigator's judgment) are not to be recorded as adverse events. However, laboratory value changes that require treatment or adjustment in current therapy are considered adverse events. Where applicable, clinical sequelae (not the laboratory abnormality) are to be recorded as the adverse event.

All protocol-required laboratory assessments, as defined in [Appendix 2](#), must be conducted in accordance with the laboratory manual and the Schedule of Activities.

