10.3.2.3.3 Laboratory Test Results

The analyses of safety laboratory endpoints will include summary statistics at selected timepoints by treatment group. Shifts in grades of safety laboratory values between the baseline and the worst on-study value will be tabulated.

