2.1 Objectives and Endpoints

Objectives	Endpoints
Primary	
Phase 1b 
To evaluate the safety and tolerability of subcutaneous (SC) dose administrations of AMG 592 in subjects with active rheumatoid arthritis (RA)	Phase 1b 
Treatment-emergent adverse events.Clinically significant changes in vital signs, laboratory safety tests, and electrocardiograms (ECGs)
Phase 2a 
To evaluate the efficacy of AMG 592 at week 12 as measured by the American College of Rheumatology 20% improvement criteria (ACR 20) in adult subjects with moderate to severe RA	Phase 2a 
ACR 20 at week 12
Secondary	
Phase 1b 
To characterize the pharmacokinetic (PK) profile following treatment with AMG 592	Phase 1b 
AMG 592 serum concentration and PK parameters including, but not limited to, maximum observed concentration (C_{max}), the time of maximum observed concentration (T_{max}), and area under the concentration-time curve (AUC_{tau}) after the first and last doses.
Phase 1b 
To evaluate the incidence of anti-AMG 592 antibody formation and cross-reactivity to human IL-2.	
Anti-AMG 592 antibodies and cross-reactivity to IL-2.Anti-AMG 592 and anti-IL-2 neutralizing antibodies

Objectives	Endpoints

Phase 2a
To evaluate the effect of treatment with AMG 592 on other measures of disease activity at week 12	
Phase 2a
ACR 50/70 at week 12Disease activity score (28 joints) calculated using the erythrocyte sedimentation rate formula (DAS28-ESR) and change from baseline at week 12Disease activity score (28 joints) calculated using the C-reactive protein formula (DAS-28-CRP) and change from baseline at week 12

To evaluate the safety of AMG 592	
Treatment-emergent adverse events.Clinically significant changes in vital signs, laboratory safety tests

To characterize the PK of AMG 592 in subjects with RA	
AMG 592 serum concentration and PK parameters

Exploratory

Objectives	Endpoints

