9.7.3 Analyses of Health Economic Endpoints

Not applicable for the study

10. Changes from Protocol-specified Analyses

ECG listing as planned in the protocol will not be provided because only critical data listings will be included in the CSR and summary tables planned for ECG data will be adequate to identify significant changes (if any) in ECG data.

11. Literature Citations / References

12. Prioritization of Analyses

There is no prioritization of analyses.

13. Data Not Covered by This Plan

Exploratory data not included in this plan may be analyzed at a later date or may be analyzed by a different Amgen Department.

14. Appendices

Appendix A. Technical Detail and Supplemental Information Regarding Statistical Procedures and Programs

Imputation Rules for Partial or Missing Stop Dates

If the month and year are present, impute the last day of the month. If only the year is present, impute December 31 of that year. If the stop date is entirely missing, assume the event or medication is ongoing and do not impute.

Imputation Rules for Partial or Missing Start Dates

		Stop Date							
		Complete: yyyymmdd		Partial: yyyymm		Partial: yyyy		Missing	
Start Date		<1 st Dose	≥1 st Dose	<1 st Dose yyyymm	≥1 st Dose yyyymm	<1 st Dose yyyy	≥1 st Dose yyyy		
Partial: yyyymm	=1 st Dose yyyymm	2	1	2	1	N/A	1	1	
	≠ 1 st Dose yyyymm		2		2	2	2	2	
Partial: YYYY	=1 st Dose yyyy	3	1	3	1	N/A	1	1	
	≠ 1 st Dose yyyy		3		3	3	3	3	
Missing		4	1	4	1	4	1	1	

[figure not shown]
1 = Impute the date of first dose

[figure not shown]
2 = Impute the first day of the month

[figure not shown]
3 = Impute January 1 of the year

[figure not shown]
4 = Impute January 1 of the stop year

[figure not shown]

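### SAP 9.6.3 ties both grade-based laboratory outputs to an unnamed selection of analytes, so an unreported grade 3-4 value in any other analyte has no graded or subject-level display in the study report

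*SAP*

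**What the plan says.** The phase 1b primary endpoint has a laboratory component. SAP 2.1, matching Protocol 4.1, lists "Clinically significant changes in vital signs, laboratory safety tests, and electrocardiograms (ECGs").

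For the analysis, Protocol 10.3.2.3.3 states: "Shifts in grades of safety laboratory values between the baseline and the worst on-study value will be tabulated". The word selected occurs in that section only for the timepoints of the summary statistics, not for the analytes whose grades are shifted.

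SAP 9.6.3 provides three laboratory outputs:

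- **By-visit summaries**, not restricted by analyte: "Summaries of chemistry and hematology laboratory data will include baseline value, values and change from baseline at scheduled visits". Under SAP 9.1, "Descriptive statistics on continuous measurements will include means, medians, standard deviations, and ranges".
- **Shift tables** from baseline to the maximum post-dose CTCAE grade, which "will be provided for selected laboratory parameters of interest".
- **A listing of grade 3 or higher toxicities** "for subjects with grade 3 or higher toxicity for any of the parameters included in the shift table". Its content is also confined to the shift-table parameters.

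No readable part of either document names the selected parameters or says how or when they are chosen. SAP Appendix C only points to CTCAE, and Protocol Table 12-1 lists the analytes without marking any as selected. SAP Section 10 declares one departure from the protocol: "ECG listing as planned in the protocol will not be provided because only critical data listings will be included in the CSR".

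**The concern.** One undefined choice controls both of the outputs that show laboratory toxicity by grade. A shorter set of shift tables is ordinary practice. The difficulty is the listing. A grade 3+ listing usually serves as the net for what nobody expected, and here it catches only analytes already thought interesting enough for a shift table. Even a sensible selection leaves an unexpected grade 3-4 value in another analyte outside it.

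In a small study whose primary purpose is safety, that listing is also the objective check on the investigator's judgment of what is clinically significant. For unselected analytes the report contains no such check, and Section 10 does not tell the reader that the protocol's grade-shift analysis has been reduced.

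**Working it through.** The plan gives no figure for this point, so the check follows one value through the planned outputs: a grade 3 or 4 result in a chemistry or haematology analyte that is not in the shift table.

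1. **Shift table (SAP 9.6.3).** Not shown, because the analyte is not selected.
2. **Grade 3+ listing (SAP 9.6.3).** It does not put the subject on the listing. If the subject is listed for another analyte, this value is still absent, because the listing carries shift-table parameters only.
3. **By-visit summaries (SAP 9.6.3, 9.1).** The analyte is covered. The value can appear as the minimum or maximum of a range, without grade or subject. SAP Appendix E keeps one visit per analysis window, the one nearest the target day, so a worst value at another visit in the window may not enter. Vital signs have post-baseline maximum and minimum summaries (SAP 9.6.4); laboratory data have no equivalent.
4. **Adverse event tables (SAP 9.6.2).** The value arrives here if the investigator reports it. Protocol 9.2.4 makes the investigator responsible for "recording any clinically relevant changes occurring during the study in the Event CRF", and changes needing treatment or an adjustment of therapy count as adverse events. These are CTCAE-graded and tabulated by worst grade. The same section keeps abnormalities judged not clinically significant out of adverse event recording and, where applicable, has the clinical sequela recorded in place of the laboratory finding.
5. **Dose level review (Protocol Appendix 3, SAP 7.1).** Laboratory results are reviewed, and listed or plotted. SAP 9.1 keeps such additional listings out of the Clinical Study Report.

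The exposed case is therefore specific: grade 3-4, unselected analyte, not reported as an adverse event. For that case steps 1, 2 and 4 give nothing, step 3 may give an ungraded extreme, and step 5 lies outside the report.

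**What can be counted.** Protocol Table 12-1 lists 17 chemistry analytes and 11 + 6 = 17 haematology items including the differential, 34 in all. The documents do not say how many are CTCAE-gradable or how many are selected. One subject is 1/6 = 17% of the AMG 592 group in cohort 1 or 4, and 1/12 = 8% in cohort 2 or 3. That is the weight of one case, not the chance of one.

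**Illustration on assumed inputs.** The plan's own chances of at least one event follow 1 − (1 − p)^n: n = 6 gives 82.2% and 73.8% at rates of 25% and 20%; n = 12 gives 96.8% and 93.1%; n = 36 gives 30.4% and 84.2% at 1% and 5%. All agree with Protocol 10.1.1. Now let p be the share of subjects with a grade 3+ laboratory event and q the fraction of those events in unselected analytes. Neither is in the documents. The chance that at least one of the 36 planned AMG 592 subjects has an event outside the listing is 1 − (1 − pq)^36:

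| p | q = 0.25 | q = 0.50 | q = 0.75 |
|---|---|---|---|
| 1% | 8.6% | 16.5% | 23.7% |
| 5% | 36.4% | 59.8% | 74.7% |

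Given p and q, these are upper limits for the exposed case, since events reported as adverse events must be taken off.

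**The case against.** The strongest reply starts from the endpoint. It is clinically significant change, not CTCAE grade, and Protocol 9.2.4 gives that judgment to the investigator. A change so judged reaches the adverse event tables by worst grade, whatever the analyte. In addition, concurrent transaminase and bilirubin or INR elevations meeting the Protocol Appendix 7 criteria must be reported as serious adverse events. This stands, and it confines the gap to values the investigator did not report.

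Second, the protocol sentence does not say every analyte, and Protocol 10.3.2.1 speaks of descriptive statistics for selected safety data, so SAP 9.6.3 might be read as filling in a general statement. This stands in part. The SAP is narrower than the protocol text rather than in flat contradiction with it. But Section 10 thought one dropped listing worth declaring, and a reduced grade-shift analysis for a primary endpoint component is at least as worth declaring.

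Third, the SAP is redacted and its contents list shows no Appendix B or D, so a parameter list that cannot be seen is possible. That cannot be excluded, but 9.6.3 refers to none. A list would also settle only the naming, not the restricted trigger of the listing.

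Finally, a reader might infer that the analytes will be picked after unblinded results are seen, since Protocol 7.3.2 lets sponsor staff have access. The text is silent on when the choice is made. It does not prevent a late choice, but it gives no evidence of one.

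**Conclusion.** The point holds as a gap in reporting. SAP 9.6.3 narrows the planned grade-shift analysis to unnamed parameters, makes the grade 3+ listing depend on the same selection, and leaves this undeclared. It merits correction because the restriction on the listing is a stated rule, not just missing detail, and the study's primary purpose is safety.

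Two stronger readings are not supported. A reader might infer that an unselected analyte falls out of the primary endpoint; it does not, because the adverse event route and the by-visit summaries remain. A reader might also infer that dose decisions rest on a cleaner picture than the data give; the dose level review sees the laboratory results, so nothing shows that those decisions are affected.

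The size is unknown. The illustrative chances, from 8.6% to 74.7%, depend entirely on assumed rates and shares and are not estimates. Phase 1b is descriptive, so no test or error rate is involved. The conclusion rests on the readable text of the SAP; the separate analysis plan for the dose level reviews was not available.

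**What to change.** In SAP 9.6.3, trigger the grade 3+ listing by any chemistry or haematology analyte in Protocol Table 12-1 that has a CTCAE grade, whether or not it is in the shift table, and include the triggering analyte's values in the listing. This is the essential change.

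For the shift tables, either produce them for all such analytes, or name the subset in the SAP before database lock and record the reduction in SAP Section 10 as a change from Protocol 10.3.2.3.3.

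The cost is SAP wording and some additional standard pages. No new data are needed. The downside is longer output.

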9.6.4 Vital Signs

Phase 1b

The analyses of vital signs will include summary statistics at selected time points, **post-baseline maximum/minimum and change from baseline to post-baseline maximum/minimum** by treatment group for systolic/diastolic blood pressure, heart rate and temperature.

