10.3.2.3.4 Vital Signs

The analyses of vital signs will include summary statistics at selected timepoints. Shifts in vital sign values between the baseline and the worst on-study value will be tabulated.

[figure not shown]

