9.6.6 Electrocardiogram

Phase 1b

Summaries over time and/or changes from baseline over time will be provided for all ECG parameters (PR, QRS, QTcF, QTcB, RR). Subjects' maximum change from baseline in QTcF, **and** QTcB will be categorized and the number and percentage of subjects in each group will be summarized. Subjects' maximum post baseline values will also be categorized and the number and percentage of subjects in each group will be summarized.

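### SAP 9.6.4 replaces the protocol's vital-sign shift tabulation with continuous summaries and Section 10 does not declare it, so no vital-signs output counts subjects with a marked change

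*SAP*

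**What the plan says.** - **Endpoint.** Protocol 4.1 and SAP 2.1 list two primary endpoint items for phase 1b: treatment-emergent adverse events and, separately, "Clinically significant changes in vital signs, laboratory safety tests, and electrocardiograms (ECGs". Neither section gives a criterion for a significant vital-sign change.
- **Protocol 10.3.2.3.4.** After a sentence on summary statistics, a second sentence adds: "Shifts in vital sign values between the baseline and the worst on-study value will be tabulated".
- **SAP 9.6.4.** It starts "The analyses of vital signs will include summary statistics at selected time points" and continues with "post-baseline maximum/minimum and change from baseline to post-baseline maximum/minimum", by treatment group, for blood pressure, heart rate and temperature. It has no shift table, category, criterion or subject count.
- **SAP 9.1.** This fixes what a continuous summary contains: "Descriptive statistics on continuous measurements will include means, medians, standard deviations, and ranges".
- **SAP 9.6.3 (laboratory).** "Shift tables indicating the change between the baseline and the maximum post dose CTCAE grades" are planned for selected parameters, with a listing of subjects at grade 3 or higher.
- **SAP 9.6.6 (ECG).** Each subject's maximum change in QTcF and QTcB "will be categorized and the number and percentage of subjects in each group will be summarized"; maximum post-baseline values are treated the same way.
- **SAP Section 10.** One departure from the protocol is declared: "ECG listing as planned in the protocol will not be provided because only critical data listings will be included in the CSR". Vital signs are not mentioned.

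**The concern.** The endpoint is framed in terms of changes that matter clinically, so the natural question for each dose is how many subjects had one. For laboratory tests and QTc the SAP answers with grades or categories. For vital signs it gives means, medians, SDs and ranges of extremes. These describe the group and its most extreme subject, but do not say whether one subject or several moved markedly. The protocol had planned a second kind of vital-sign output, and a reader of Section 10 would conclude that it is still coming.

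**Working it through.** **1. Is there a figure in the plan to reproduce?** None on vital signs. The only phase 1b design figures (Protocol 10.1.1) are chances of at least one affected subject, 1 − (1 − p)^n:

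- n = 6: 1 − 0.75^6 = 82.2% and 1 − 0.80^6 = 73.8% (plan: 82%, 74%)
- n = 12: 96.8% and 93.1% (plan: 97%, 93%)
- n = 36 at 1% and 5%: 30.4% and 84.2% (plan: 30%, 84%)

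All reproduce and none is in dispute. They matter here only because they supply the group sizes and because the size rationale is itself expressed in affected subjects.

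**2. Protocol against SAP.** The protocol gives vital signs two outputs, summary statistics and a shift tabulation. The SAP keeps the first. In place of the second it has continuous summaries of the maximum, the minimum and the change to each. A baseline-to-extreme analysis therefore remains, but without a tabulation of subjects.

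**3. Can the count be recovered from the SAP's statistics?** Take n = 6, the planned AMG 592 number in cohorts 1 and 4, assuming results are shown by dose cohort. Assume a cut-off of 30 units on the maximum change; the documents give none. Consider two possible sets of changes:

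- A = {0, 0, 6, 16, 30, 40}
- B = {0, 2, 2, 20, 28, 40}

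| Statistic | A | B |
|---|---|---|
| Sum; mean | 92; 92/6 = 15.33 | 92; 15.33 |
| Median | (6 + 16)/2 = 11 | (2 + 20)/2 = 11 |
| Sum of squares | 36 + 256 + 900 + 1600 = 2792 | 4 + 4 + 400 + 784 + 1600 = 2792 |
| SD = √[(2792 − 92²/6)/5] | √276.27 = 16.62 | 16.62 |
| Range | 0 to 40 | 0 to 40 |
| Subjects at or above 30 | **2 of 6 (33.3%)** | **1 of 6 (16.7%)** |

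The change table under SAP 9.6.4 would be identical for A and B.

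**4. Does a larger cohort remove the problem?** No. Taking every value twice gives n = 12, the planned AMG 592 number in cohorts 2 and 3. Mean, median and range are unchanged, and the SD is √[(5584 − 184²/12)/11] = √251.15 = 15.85 for both sets. The counts become 4 and 2.

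**5. Limit of the argument.** Sometimes the four statistics do settle the count. With changes {−40, 0, 0, 0, 0, 0} the mean is −6.67 and the range is −40 to 0. The other five values cannot be positive and must sum to zero, so all are zero and exactly one subject is affected. The claim is therefore that the count is not determined in general, not that it never is.

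**The case against.** **The SAP still analyses baseline to worst.** A reader might infer from the first words of SAP 9.6.4 that this analysis was abandoned. It was not. The section continues with the change to both extremes, and SAP Appendix F shows that the text was added deliberately. The protocol also speaks of shifts in grades for laboratory tests but shifts in values for vital signs, so a continuous change can be argued to be one way of carrying out the plan. This stands to the extent that the SAP has replaced the tabulation rather than removed the analysis. It does not explain why the protocol gave the shift tabulation its own sentence beside summary statistics, or why Section 10 is silent.

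**Adverse event tables already count subjects.** A reader might infer that no output of any kind counts clinically significant vital-sign changes, so that the primary endpoint cannot be reported. The documents do not support that. Protocol Appendix 4 makes vital-sign findings that the investigator judges clinically significant adverse events, and SAP 9.6.2 tabulates subject incidence. But those counts depend on investigator judgement and are scattered over preferred terms. Appendix 4 also asks for the diagnosis rather than the component signs, so a blood-pressure change within a diagnosed reaction need not appear as a vital-sign event. The endpoint lists vital-sign changes separately from adverse events.

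**Counts are partial elsewhere too.** Laboratory shifts cover selected parameters only. SAP 9.6.6 names only QTcF and QTcB for change categories and has no cross-tabulation by baseline. This is true, but each of those components has some categorical output of its own and vital signs have none.

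**Individual data are seen.** SAP 7.1 has vital signs listed or plotted for the dose level review meetings. This helps dosing decisions, but SAP 9.1 keeps such additional listings out of the clinical study report.

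**Conclusion.** The point holds in limited form. SAP 9.6.4 substitutes continuous summaries for the protocol's shift tabulation, Section 10 does not declare it, and no vital-signs output counts subjects with a marked change. In the worked example that leaves 1 of 6 indistinguishable from 2 of 6, and 2 of 12 from 4 of 12. Those figures rest on an assumed cut-off of 30 and on reporting by dose cohort.

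The consequence is moderate. Phase 1b is descriptive and no test or decision threshold depends on this table. A count would itself be imprecise: the exact 95% interval is 0.4% to 64.1% for 1 of 6 and 4.3% to 77.7% for 2 of 6. Its value is in describing a named component of the primary endpoint, and in keeping the list of departures from the protocol complete. It should be corrected before database lock.

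**What to change.** In SAP 9.6.4, keep the maximum and minimum summaries and add one table. For each vital sign and treatment group, give the number and percentage of subjects:

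- by prespecified category of worst post-baseline value, set against baseline category, as the protocol's shift tabulation implies, and in both directions where either a high or a low value can be the worst;
- by prespecified category of maximum change from baseline.

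The sponsor's clinical team should set the categories before unblinded summaries are produced. If the sponsor prefers continuous summaries only, SAP Section 10 should declare the change and justify it.

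The same edit should settle respiratory rate, which Protocol 9.2.3.2 requires but SAP 9.6.4 does not name.

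The cost is SAP wording and one extra table from data already collected.
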